7.5. Telephone Follow-Up

If subjects are unable to return for follow-up visits to the investigator's office, they may be contacted by telephone to assess their status. Subjects will be asked whether the study device is in place or has been revised, and patient satisfaction will be assessed. This information will be recorded on the corresponding CRF.

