3. STUDY DESIGN

This is a prospective, multicenter, observational study that is currently in the follow-up data collection phase. Five of the seven study sites that contributed data to the PMA cohort will participate in this PAS. The two sites that will not participate in the PAS did not enroll any R3 Biolox delta Ceramic Acetabular System (DOD) PMA subjects, as such their data is not suitable for this PAS. The DOD treatment arm of the PMA Cohort included 137 DOD subjects.

Of the 137 DOD subjects included in the PMA Cohort, one died and one was revised by the 3-year follow-up interval. A total of 135 subjects are therefore eligible for this PAS study and all attempts will be made to continue follow-up on all subjects through the 10-year postoperative interval. Telephone follow-up for determination of device survival or revision status, and patient satisfaction in cases where subjects fail to return for follow-up visits will be conducted.

Smith & Nephew - Advanced Surgical Devices Division

Post-Approval Study of the R3 Biolox delta Ceramic Acetabular System – Europe	Protocol Number: R3H01/02/01/2017/Version2.0
	PMA Number P150030
	ADDENDUM Page: 10 of 25

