7.2. Conditions for Study Termination

All reasonable efforts should be made to retain the subjects for the 10-year duration of this study. If the subject has a revision of any component, the subject will be terminated from the study.

A. Voluntary Withdrawal

Study participation is voluntary and subjects may withdraw at any point during the study without giving their reason for doing so. A study termination form will be completed for all subjects who do not finish the study, to document the reason for the withdrawal in the CRF.

B. Lost to Follow-Up

Some actively enrolled subjects will not return for follow-up exams due to a variety of reasons. Study personnel will make a reasonable effort to contact the subject and document the following contact attempts prior to declaring a subject to be lost to follow-up: the subject has been contacted according to the study sites policies, but no less than 2 documented phone contacts and 1 certified letter without response. Copies of all attempts to reach the subjects per regular mail or email and/or the attempts to contact the subject via other means should be documented and such documentation should be kept with the subjects CRF. A subject will be considered lost to follow-up if he/she does not appear for the scheduled study visit for 2 consecutive visits and study personnel are unable to contact the subject.

C. Study Termination by Investigator/Sponsor

The Investigator **may** withdraw subjects from the study for many reasons, including but not limited to the following:

- subject noncompliance to study schematic
- subject lost to follow-up

The Investigator **should** withdraw subjects from the study:

- in case any component of the original hardware is revised/exchanged
- if the Investigator or the Sponsor stops the study for any reason

For each case, information will be obtained on the Study Termination Form, detailing circumstances leading to the withdrawal.

D. Study Site Discontinuation

Smith & Nephew - Advanced Surgical Devices Division

Post-Approval Study of the R3 Biolox delta Ceramic Acetabular System – Europe	Protocol Number: R3H01/02/01/2017/Version2.0 PMA Number P150030 ADDENDUM Page: 15 of 25
--	---

A specific study site in this multicenter study may also warrant termination under the following conditions:

- non-compliance to Good Clinical Practice (GCP) or protocol
- major protocol deviations
- inaccurate or incomplete data
- unsafe or unethical practices

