4 STUDY OBJECTIVES

The objective of this study is to determine the long-term safety and effectiveness of the R3 Acetabular System by analysing the clinical, radiographic responses and the adverse event rates for

CONFIDENTIAL AND PROPRIETARY

This document contains information that is confidential and proprietary to Smith & Nephew PLC and Smith & Nephew, Inc. and is intended for use only by Smith+Nephew and its manufacturer. It shall not be reproduced or copied in whole or in part, nor shall the contents be disclosed by any means without prior written permission from Smith+Nephew, nor shall anyone make any use of it that is contrary to the expressed or implied wishes of Smith+Nephew.

Statistical Analysis Plan

A prospective, multicenter, non-randomized, clinical outcomes study of the R3[◊] Acetabular System in patients with degenerative hip disease

Number:
R3H01/02/01/2017
ST: 1103
Version: 3.0
Page: 7 of 18

patients undergoing primary total hip arthroplasty using the R3 Hip System (R3 Acetabular System). The study hypothesis is as follows: implant survivorship (Kaplan-Meier) (revision for any reason) of the R3 cup is at least 97% at 3 years, 95% at 5 years, 93% at 7 years, and 90% at 10 years follow-up.

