7.3 Handling of Missing, Incomplete and Repeat Data

For the primary endpoint, subjects with hips that are prematurely discontinued from the study due to death or loss to follow-up would be censored on the last known date on-study.

Specific instructions for handling missing PROMs is described in Section 7.4. If $\geq 10\%$ of postoperative UCLA, HOOS or HHS scores at more than 2 of the postoperative follow-up time points are missing, only their observed data will be summarized using the change from preoperative to each postoperative time point as the endpoints of interest.

CONFIDENTIAL AND PROPRIETARY

This document contains information that is confidential and proprietary to Smith & Nephew PLC and Smith & Nephew, Inc. and is intended for use only by Smith+Nephew and its manufacturer. It shall not be reproduced or copied in whole or in part, nor shall the contents be disclosed by any means without prior written permission from Smith+Nephew, nor shall anyone make any use of it that is contrary to the expressed or implied wishes of Smith+Nephew.

Statistical Analysis Plan

A prospective, multicenter, non-randomized, clinical outcomes study of the R3[◊] Acetabular System in patients with degenerative hip disease

Number:
R3H01/02/01/2017
ST: 1103
Version: 3.0
Page: 10 of 18

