	Moderate pain; tolerable but makes concessions to pain. Some limitation of ordinary activity or work. May require occasional pain medication stronger than aspirin	20	
	Marked pain, serious limitation of activities	10	
	Totally disabled, crippled, pain in bed, bedridden	0	
Limp	None	11	Function Domain (0 to 47)
	Slight	8	
	Moderate	5	
	Severe	0	
Support	None	11	{Sum of all items within subdomain}
	Single cane for long walks	7	
	Single cane most of the time	5	
	One crutch	3	
	Two canes	2	
	Two crutches or not able to walk	0	
Distance walked	Unlimited	11	
	Six blocks	8	
	Daily shopping	5	
	Indoors only	2	
	Bed and chair only	0	
Sitting	Comfortably in ordinary chair	5	
	On a high chair for 30 minutes	3	
	Unable to sit comfortably in any chair	0	

CONFIDENTIAL AND PROPRIETARY

This document contains information that is confidential and proprietary to Smith & Nephew PLC and Smith & Nephew, Inc. and is intended for use only by Smith+Nephew and its manufacturer. It shall not be reproduced or copied in whole or in part, nor shall the contents be disclosed by any means without prior written permission from Smith+Nephew, nor shall anyone make any use of it that is contrary to the expressed or implied wishes of Smith+Nephew.

Statistical Analysis Plan

A prospective, multicenter, non-randomized, clinical outcomes study of the R3[◊] Acetabular System in patients with degenerative hip disease

Number:
R3H01/02/01/2017
ST: 1103
Version: 3.0
Page: 13 of 18

Public transportation	Yes, possible No, unable	1 0	
Stairs	Normally without using a railing Normally using a railing In any manner Unable to do stairs	4 2 1 0	
Socks/Shoes	With ease With difficulty Unable	4 2 0	
Range of Motion (ROM)	Flexion = FLEX+EXT-FLEX_ZERO Movement = ABD+ADD-ABD_ZERO Rotation = ER+IR-ER_ZERO	N/A N/A N/A	
ROM subscore	Flexion+Movement+Rotation 0 to 29 30 to 59 60 to 99 100 to 159 160 to 209 ≥ 209	0 1 2 3 4 5	Range of Motion Domain (0 to 5)
Leg Length Difference (in mm)	None Ipsilateral longer (LL_DIF_LONG) Ipsilateral shorter (LL_DIF_SHORT)	N/A N/A N/A	
Absence of Deformity (AOD)	IF (FLEX_ZERO = . OR FLEX_ZERO < 31) AND (ABD_ZERO = . OR ABD_ZERO < 11) AND (ER_ZERO = . OR ER_ZERO < 11) AND LL_DIF_LONG < 33 AND LL_DIF_SHORT < 33 THEN AODScore = 4	0 or 4	Absence of Deformity Domain (0 to 4)
Total HHS		Sum of all domain scores per subject	Sum of all domain scores per subject

CONFIDENTIAL AND PROPRIETARY

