7.6 Disposition Data

Hip accountability will be summarized by study visit (see Table 1 for visit schedule) for the number of hips that are theoretically due, subjects who died, hips that were revised, hips terminated from the study for any reason. Additional information will include but not limited to number of subjects presenting at each visit, number of hips expected at each visit and follow up rate.

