7.10 Analysis of Secondary Endpoints

- HOOS sub-scores, HHS (and its subscores) and UCLA would be summarized using descriptive summary characteristics for continuous variables at the preoperative and all postoperative time points. Changes from the preoperative (baseline) to subsequent postoperative visit(s) would also be summarized using descriptive statistics for continuous

CONFIDENTIAL AND PROPRIETARY

This document contains information that is confidential and proprietary to Smith & Nephew PLC and Smith & Nephew, Inc. and is intended for use only by Smith+Nephew and its manufacturer. It shall not be reproduced or copied in whole or in part, nor shall the contents be disclosed by any means without prior written permission from Smith+Nephew, nor shall anyone make any use of it that is contrary to the expressed or implied wishes of Smith+Nephew.

Statistical Analysis Plan

A prospective, multicenter, non-randomized, clinical outcomes study of the R3[◊] Acetabular System in patients with degenerative hip disease

Number:
R3H01/02/01/2017
ST: 1103
Version: 3.0
Page: 16 of 18

variables. Mixed Model Repeated Measures (MMRM) with a missing at random (MAR) assumption to account for the pattern of missing longitudinal data would be used to analyze the Patient Reported Outcome Measures (PROMs) to compare the scores between the preoperative and postoperative visit time points. The model will include fixed effect term for visit. The Kenward Rogers denominator degrees of freedom would be used coupled with a specification for an unstructured covariance matrix. The test of any of the comparisons between the preoperative and postoperative visits will be concluded to be statistically significant if $p < 0.05$. Model-based Means or Least Square (LS) Means for all visits as well as the differences between each postoperative versus the preoperative visit and their 95% two-sided Confidence Intervals (CI) would be presented. Should greater than 10% of any of the PROMs data on at least at two of the postoperative timepoints be missing, MMRM would not be used.

- For radiographic findings, patient satisfaction and Trendelenburg, descriptive summary statistics for categorical variables such as frequency (n) and percentage (%) will be presented by visit.

The secondary endpoint analysis will be performed only on the FAS population.

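### The SAP plans an MMRM to deal with missing PROM scores, then withdraws it once missingness exceeds 10% at two visits, leaving only descriptive observed-case summaries

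*SAP*

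**What the plan says.** SAP Section 7.10 analyses the PROMs (HOOS subscores, HHS, UCLA) with an MMRM under MAR. Visit is the only fixed effect, with an unstructured covariance and Kenward-Roger degrees of freedom. The outputs are least-squares means by visit, differences from preoperative with 95% intervals, and tests at the 5% level. Scores and changes at each visit are also summarised descriptively. All of this is on the FAS only.

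The same section then adds that if more "than 10% of any of the PROMs data on at least at two of the postoperative timepoints be missing, MMRM would not be used".

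Section 7.3 has its own rule: if 10% or more of UCLA, HOOS or HHS "scores at more than 2 of the postoperative follow-up time points are missing, only their observed data will be summarized", as change from preoperative.

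Neither section names a replacement model, an imputation or a sensitivity analysis, and neither says what the 10% is a percentage of. Section 7.3 refers to Section 7.4 for missing PROMs. The part of 7.4 that could be read gives item-level HOOS scoring rules and nothing on missed visits; the text between Table 4 and Section 7.5 was not available for this check.

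Three other places bear on the point:
- Protocol Section 9 says that multiple imputation will be used for missing data. SAP Section 7.14, the list of changes from the protocol, does not mention its replacement.
- SAP Section 7.6 will tabulate, by visit, "the number of hips that are theoretically due, subjects who died, hips that were revised, hips terminated from the study for any reason".
- Protocol Section 7.5 allows telephone contact instead of a visit: "Subjects will be asked whether the study device is in place or has been revised, and patient satisfaction will be assessed". No PROM score is mentioned there.

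**The concern.** The MMRM was chosen because longitudinal scores would be incomplete. It uses each hip's earlier scores to allow for later gaps, which is legitimate under MAR. An observed-case mean does not, and in general it needs missingness unrelated to any score. The rule therefore moves from the weaker assumption to the stronger one as the amount of missing data grows, and drops the planned model-based inference with it. More missing data makes any method depend more on its assumptions, but that is no reason to prefer the method with the stronger assumption.

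At stake is the description of late function (HHS, HOOS, UCLA at 7 and 10 years), which could come to describe only those who returned. Telephone follow-up makes this plausible even with good retention, because a hip can count for survivorship without a PROM at that visit.

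**Working it through.** **1. When the rules fire.** The documents give no PROM missingness rate, so assume a constant annual loss r. Missing at t years is 1 - (1 - r)^t, and 10% is reached at r = 1 - 0.9^(1/t):
- 10 years: 1 - 0.9^(1/10) = 1.05% per year
- 7 years: 1 - 0.9^(1/7) = 1.49% per year
- 5 years: 1 - 0.9^(1/5) = 2.09% per year

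Section 7.10 needs two visits (7 and 10 years), so it fires from about 1.5% per year. Section 7.3 needs three (5, 7 and 10 years), so it fires from about 2.1% per year.

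| Annual loss | 5 y | 7 y | 10 y | 7.10 bars MMRM | 7.3 fires |
|---|---|---|---|---|---|
| 1.0% | 4.9% | 6.8% | 9.6% | no | no |
| 1.5% | 7.3% | 10.04% | 14.0% | yes | no |
| 2.0% | 9.6% | 13.2% | 18.3% | yes | no |
| 2.5% | 11.9% | 16.2% | 22.4% | yes | yes |
| 3.0% | 14.1% | 19.2% | 26.3% | yes | yes |

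**2. The two rules side by side.** Section 7.10 uses more than 10% at two or more visits; Section 7.3 uses 10% or more at more than two. With over 10% at exactly two visits, the MMRM is barred but the 7.3 fallback is not invoked. The 1.5% and 2.0% rows are such cases. Only the descriptive part of 7.10 is then left.

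**3. Size of the bias in 10-year HHS change.** All inputs are assumptions except the score maximum of 100 (44 + 47 + 5 + 4, SAP Section 7.4, Table 4). The main inputs were preoperative mean about 50 and SD 15; change 39 and postoperative SD 14 before capping at 100, so a true change of roughly 37 after capping; monotone MAR dropout from 1 year on, with lower last scores more likely to drop out (log-hazard slope 0.5 or 1.0 per SD); and 15-26% missing at 10 years. The MMRM was represented by maximum likelihood with free visit means and unstructured covariance.

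Observed-case bias, in points:
- pre-post correlation 0.3, constant postoperative correlation 0.5 or 0.7: +0.1 to +1.3
- pre-post 0.5, postoperative 0.5: -0.1 to -0.5
- pre-post 0.5, postoperative 0.7: +0.1 to +0.25
- postoperative correlation decaying by visit (0.7 between adjacent visits): 0.0 to +0.2 at pre-post 0.3, and -0.2 to -0.7 at pre-post 0.5
- widest range over the correlations tried: about -0.9 to +1.9

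The MMRM stayed within 0.07 point of zero under MAR.

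**4. Why the sign can turn.** Suppose those who remain have an earlier postoperative score higher by d SDs. For normal scores and a single selection step, before capping, the bias in change is about d x (SD_post x r_post - SD_pre x r_pre). With r_post = 0.5 and r_pre = 0.3 the bracket is 14 x 0.5 - 15 x 0.3 = +2.5. With both at 0.5 it is 14 x 0.5 - 15 x 0.5 = -0.5. Low scorers who leave also tend to have had low preoperative scores, so their loss raises both means and the difference can go either way.

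**5. Missing not at random.** With dropout driven by the current unseen score (pre-post correlation 0.3), observed-case bias was +0.2 to +2.3 and MMRM bias +0.2 to +2.4. The MMRM was less biased in all 36 settings at postoperative correlation 0.7, but more biased in 24 of 36 at 0.5.

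**The case against.** The strongest reply is that little depends on this. The endpoints are secondary, no PROM success criterion exists, and the Kaplan-Meier analysis is untouched. The largest bias under MAR, 1.9 points, is about 5% of the change (1.9/37). Deleting a prespecified rule after last subject last visit (SAP Section 6.3) also has a cost in credibility. All of this stands and limits the weight of the point. It does not justify the rule, which works against its own purpose whatever the size of the bias.

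Several stronger readings are tempting but not supported:
- *The late PROM results would look too good.* The direction depends on correlations that the documents do not give, and it can be negative.
- *The rule will fire.* No missingness rate is stated.
- *Only change scores would be left, with no intervals at all.* Section 7.10 also summarises the scores at each visit, and Section 7.1 allows 95% intervals where appropriate. What is lost is the model-based means, intervals and tests.
- *The rules clash at exactly 10% missing.* On the wording, 7.3 would fire at three such visits and 7.10 would not. Whether exactly 10% can occur depends on the number of hips in the FAS, which is not given; the 512 enrolled is not that number. The mismatch at exactly two visits needs no such coincidence.
- *The MMRM cures the missing-data problem.* Under missing not at random neither method is safe.
- *Revision ends PROM collection for everyone.* The statement "If the subject has a revision of any component, the subject will be terminated from the study" is in the protocol addendum and covers the PAS cohort only. It does show that the undefined denominator matters, since visits after revision may or may not be counted as missing.

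**Conclusion.** The point holds: the cut-offs in Sections 7.3 and 7.10 withdraw the missing-data method when missingness becomes material, and they disagree with each other. That much follows from the text alone. The rest rests on assumptions. Under a constant loss, about 1.5% per year fires 7.10 and about 2.1% fires 7.3. Under MAR with 15-26% missing, the observed-case 10-year HHS change is off by about -0.9 to +1.9 points in either direction, on a change of roughly 37, while the MMRM is essentially unbiased; other correlations would give other limits. The effect is modest and confined to secondary endpoints. The change should be made because the better analysis is already specified and costs little. Separately, replacing the protocol's multiple imputation without listing it in Section 7.14 is an undisclosed departure whether or not the rule fires.

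**What to change.** Amend the SAP, if possible before PROM missingness is tabulated or PROM data are analysed; if that has already happened, say so.

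1. Delete the cut-off sentences in Sections 7.3 and 7.10.
2. State in 7.10: *The MMRM is fitted to all PROM scores observed in the FAS, whatever the proportion missing. Observed-case scores and changes from preoperative are shown beside it as supportive.*
3. Report missing PROMs per visit against the hips expected under Section 7.6, with deaths and revisions shown separately. State that the MMRM means treat visits after death or revision as MAR, and so describe outcome as if the hip were still under follow-up.
4. Record in Section 7.14 that the cut-offs were removed after last subject last visit, with date and reason, and that the MMRM replaces the multiple imputation of Protocol Section 9.

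A sensitivity analysis for missing not at random would be useful but is optional.

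The cost is a late, disclosed amendment and a little more analysis work: one model per score and one missingness table. No new data are needed, and version 3.0 is itself an amendment.

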7.11 Analysis of Safety Endpoints

An overall summary AE table that would summarize as number (n) and percentages (%), the overall incidence according to subjects (and hips) with at least one AE; subjects (and hips) with at least one AE by worst severity (mild, moderate, or severe), by worst outcome (resolved, ongoing/unresolved, death or removal/revision of components), worse relatedness to device, SAEs, ADEs, SADEs, ASADEs and, USADEs. Classification of AEs would also be summarized using ISO classifications. A data listing with all AEs (and their classifications) reported on-study will be presented. Finally, the incidence of device-and/or procedure related AE by their type will be presented too.

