4.2. Safety Measures

Safety will be measured by assessing all adverse events experienced by patients related or probably related to the study device. Adverse events will be documented at the intra-operative and all postoperative evaluation intervals to determine the safety profile of the device. The incidence of surgery- and device-related events such as device revision, component failure, malfunction, migration, subluxation, dislocation, loosening, nerve damage, deep infection, deep vein thrombosis, pulmonary embolism, or bone breakage/fracture will be collected. Some events may not be evident until after a long-term follow-up such as evidence of severe osteolysis, excessive articular surface wear, or significant debris production. All adverse events in study patients between enrollment and ten years shall be reported at the time of occurrence. Efficacy and safety measurement will be performed as summarized in the study schematic presented in Table 1.

5. Study Population

This clinical study can fulfill its objectives only if appropriate subjects are enrolled. All relevant medical and non-medical

conditions should be taken into consideration when deciding whether a particular patient is suitable.

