6 STATISTICAL CONSIDERATIONS

6.1 Determination of Sample Size

The target enrollment during this study was 500 patients however 512 subjects have been enrolled. This number of patients leads to representative results with a greater precision of the survival rates, i.e. small confidence intervals.

The sample size is large enough to satisfy pseudo-regulatory requirements set-forth in individual European countries such as the Orthopaedic Data Evaluation Panel¹ (ODEP) and the National Institute for Clinical Excellence (NICE) requirements². According to the ODEP criteria for categorizing products in relation to NICE's long-term benchmarks for hip replacements, a level A study (strongest evidence) requires an initial cohort of 500 patients or more.

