7.2 Analysis Populations

The following are the analysis populations used in summarizing all tables:

Safety Analysis Population (SAF)

This will include all subjects (Hips) enrolled and implanted with the study device in the study.

Full Analysis Set (FAS)

The FAS population will include all subjects (Hips) in the SAF with at least one postoperative assessment on any of the Patient Reported Outcome Measures (PROMs).

Per Protocol (PP) Population

The PP population will include all subjects (Hips) in FAS, who have no significant protocol deviations and satisfy all study eligibility criteria and the inclusion/exclusion criteria. Significant protocol deviations leading to removal from the PP population will be determined and finalized prior to the final analyses at 10 years. The final assignment of a subject to the PP population will be established after all protocol deviations have been reviewed and evaluated. Subjects excluded from the PP will be documented/listed together with their reason(s) for exclusion.

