7.9 Analysis of Primary Endpoint

The Kaplan-Meier survival estimate would be used to estimate implant survivorship. Time to device revision will be the endpoint of interest to estimate the implant survivorship. Implant survival time (in months) is computed as: (Event Date – Operative Date+1)/30.4375.

Implanted hips that continue until study completion without an on-study revision will be censored at their last known date of participation in the study. Any premature hip discontinuation from study due to a subject's death or any other reason will be censored on the date of this discontinuation. A subject who is lost to follow-up will be censored at the subject's last known contact date. The Cumulative proportion of implant survivorship at 36 months (3-year), 60 months (5 years), 84 months (7 years) and 120 months (10 years) will be estimated and displayed accordingly. These Kaplan-Meier estimates will be provided with their corresponding two-sided 95% Confidence Intervals (CIs). If feasible, Kaplan-Meier survival graphs will be displayed to graphically illustrate implant survivorship over the study duration.

For the a-priori protocol-specified hypothesis, if the lower bound of 95% two-sided CIs at 3 years, 5 years, 7 years and 10 years are not less than 97%, 95%, 93% and 90% respectively, then we conclude that implant survivorship of the R3 cup is at least 97% at 3 years, 95% at 5 years, 93% at 7 years, and 90% at 10 years follow-up respectively.

The primary endpoint analysis will be performed on the FAS population. As sensitivity analysis, the same analysis will be performed on the PP population.

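### SAP 7.11 reports non-revision adverse events over 10 years as pooled n (%) with no account of time followed, so withdrawal and loss pull the percentages below the 10-year risk, most for late events

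*SAP*

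**What the plan says.** SAP 7.11 plans an overall adverse event (AE) table that will "summarize as number (n) and percentages (%), the overall incidence according to subjects (and hips) with at least one AE". It is broken down by worst severity, outcome, relatedness and seriousness, with ISO classes and a full listing. It adds that "the incidence of device-and/or procedure related AE by their type will be presented too". The section names no analysis population and gives no time window, person-time, number at risk or confidence interval.

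The nearest population is the Safety Analysis Population (SAF) in SAP 7.2: "This will include all subjects (Hips) enrolled and implanted with the study device in the study". Length of follow-up plays no part in that definition.

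Protocol 4.2 sets the collection period: "All adverse events in study patients between enrollment and ten years shall be reported at the time of occurrence". It also warns that "Some events may not be evident until after a long-term follow-up such as evidence of severe osteolysis", and names excessive articular wear and significant debris alongside.

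Revision is treated differently. SAP 7.9 uses Kaplan-Meier with 95% CIs at 3, 5, 7 and 10 years and states that "A subject who is lost to follow-up will be censored at the subject's last known contact date". The rule for death and loss in SAP 7.3 is limited to the primary endpoint.

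**The concern.** The study objective is long-term safety, and Protocol 5.5 accepts that some subjects will stop attending. A pooled percentage with a fixed denominator counts a subject lost at year 1 in the same way as one observed without the event for 10 years. Whatever happened after the loss cannot enter the numerator.

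The effect grows with the delay between operation and event, because fewer subjects are then still observed. The events that Protocol 4.2 singles out as possibly late are therefore the most affected. The same report would place a revision figure adjusted for follow-up beside AE percentages that are not. A reader could take both as 10-year risks, when only the first is.

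**Working it through.** The documents state no AE rate, 10-year loss rate or precision figure for safety, so there is no planned figure to reproduce. What follows is an illustration.

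**Inputs from the documents**
- SAP 6.1: "however 512 subjects have been enrolled". The 512 is used only to turn percentages into counts.
- AE collection to 10 years (Protocol 4.2).
- Denominator: all implanted (SAP 7.2), inferred because 7.11 names none.

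**Assumptions**
- True 10-year risk p = 5%, which is 512 × 0.05 = 25.6 subjects.
- Total loss L of 10% to 40% by year 10, at a constant rate and independent of events.
- No deaths at this stage.

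**Formula.** The expected crude proportion is the integral of G(t) dF(t) from 0 to 10 years, where G(t) = (1 − L)^(t/10) is the share still observed and F is the event-time distribution. If the event hazard is constant between years a and b and zero elsewhere, let H = −ln(1 − p) and m = −ln(1 − L) × (b − a)/10. Then

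crude = G(a) × H/(H + m) × [1 − (1 − p) × exp(−m)].

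**Worked case, L = 20%.** H = −ln(0.95) = 0.0513.
- Constant hazard, years 0 to 10: G(0) = 1 and m = 0.2231. Crude = 0.0513/0.2744 × (1 − 0.95 × 0.80) = 0.1869 × 0.24 = 4.49%.
- Only after year 5: G(5) = 0.8944 and m = 0.1116. Crude = 0.8944 × 0.0513/0.1629 × (1 − 0.95 × 0.8944) = 4.23%.

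**Results, true risk 5% (change relative to 5% in brackets)**

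| Total loss | First 3 months only | Constant hazard | Only after year 5 |
|---|---|---|---|
| 10% | 4.99% | 4.75% (−5%) | 4.62% (−8%) |
| 20% | 4.99% | 4.49% (−10%) | 4.23% (−15%) |
| 30% | 4.98% | 4.21% (−16%) | 3.83% (−23%) |
| 40% | 4.97% (−1%) | 3.92% (−22%) | 3.42% (−32%) |

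At 40% loss, 17.5 of the 25.6 late events would be seen. The relative shortfalls are nearly the same for true risks of 2% and 10%.

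**Adding deaths.** Take 10% deaths and 20% loss, with the event arising only after year 5:
- one minus Kaplan-Meier, which treats death as censoring: 5.00%
- Aalen-Johansen cumulative incidence, with death competing: 4.62%
- crude percentage: 3.92%

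Against Aalen-Johansen the shortfall is 1 − 3.92/4.62 = 15%, the same as with 20% loss and no deaths. With deaths only and no loss, the crude percentage equals Aalen-Johansen (4.62%). The bias comes from loss and withdrawal.

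**The case against.** **The plan already takes some account of follow-up.** Revision has Kaplan-Meier estimates (SAP 7.9), radiographic findings are tabulated by visit (7.10), and accountability is shown by visit with deaths, revisions, terminations and follow-up rate (7.6). This stands. It confines the point to non-revision AEs, and bone changes seen on films may already appear in the by-visit tables. But nothing links the accountability table to the AE percentages.

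**Deaths.** A reader might infer that subjects who die are also counted as event-free and add to the bias. The documents do not support that. Death meets the serious adverse event (SAE) definition in Protocol 8.1 and is a worst-outcome category in SAP 7.11, so a reported death is an event in the any-AE and SAE rows. For any other event, dying first is a competing event and causes no shortfall against the cumulative incidence.

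**Late events.** A reader might take Protocol 4.2 to say that these events occur only late, or that dislocation is among them. It says only that some events may become evident late, and it lists dislocation separately among general surgery- and device-related events.

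**Size.** No 10-year loss rate is given. The only early count is one death and one revision among 137 ceramic-on-ceramic subjects by 3 years (addendum, section 3), which says nothing about losses. The percentages above are therefore conditional. Nor does the shortfall equal the loss rate: 20% loss costs 10% or 15%, depending on timing.

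**Design.** This is a single-arm study with no safety hypothesis, and n (%) correctly describes the events observed. That is true and a reason to keep the tables, but the observed percentage is still not a 10-year risk.

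**Conclusion.** The point holds for non-revision AEs. With a fixed all-implanted denominator and incomplete follow-up, the SAP 7.11 percentages understate 10-year risk. The shortfall is negligible for perioperative events and largest for late ones. As an illustration with loss only, it is about 10% (constant hazard) and 15% (after year 5) in relative terms at 20% loss, and about 22% and 32% at 40% loss.

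This rests on three things: the inferred denominator, an assumed loss rate, and loss independent of events. The direction is firm under independence. If those lost differ in risk from those who stay, the size changes and a follow-up-adjusted estimate is not fully protected either. The primary endpoint is untouched. This is an inexpensive improvement to the long-term safety result and does not invalidate the plan.

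**What to change.** In SAP 7.11:
1. Keep the n (%) tables and name the SAF as their population.
2. Add Aalen-Johansen cumulative incidence, with death as a competing event, 95% CIs and numbers at risk at 1, 3, 5, 7 and 10 years. Do this for first SAE other than death, first adverse device effect and first serious adverse device effect, first device- or procedure-related event, and the late events named in Protocol 4.2 when reported as AEs. If the SAE row is to include fatal SAEs, count death there as an event.
3. Measure time from operation to AE onset, which Protocol 8.2 already requires to be recorded. For events found on films, use the detection date and say so, because visits are two to three years apart after year 1.
4. Censor at the last contact at which AEs were assessed, taken from visit records. Telephone contact will not serve by default: Protocol 7.5 and addendum 6.3 specify questions on revision status and satisfaction only.
5. Quote these estimates, not the pooled percentages, as the 10-year safety result.

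The cost is one extra set of tables, one derived censoring date and slightly less favourable percentages. No new data collection is needed.
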